Sperm Selection by Microfluidic Separation Improves Embryo Quality

NCT03085433

Document Date: 3/17/2017

Title: Microfluidic Separation Reduces Sperm DNA Damage and Improves Embryo Quality

Background/Significance

More than 70 million couples worldwide are infertile and up to 40 million are actively seeking infertility care. In the year 2013, a total of 160,521 assisted reproductive technology (ART) procedures were performed in the United States (Sunderam *et al*, 2015). Isolation of motile and morphologically normal sperm is an integral part of assisted reproduction. Traditional sperm processing for assisted reproduction involves centrifugation and “swim up” techniques that employ a density gradient to isolate motile sperm. However, studies have suggested that centrifugation induces reactive oxygen species and DNA damage (Malvezzi *et al*, 2014; Wang *et al*, 2014). Increased sperm DNA damage has been associated with poor outcomes in assisted reproduction, including lower fertilization rates, impaired embryo progression, and decreased pregnancy rates (Virro *et al*, 2004; Benchaib *et al* 2007; Simon *et al* 2014).

In contrast, microfluidic-based sperm sorting has the capability of selectively isolating highly motile, morphologically normal sperm with high DNA integrity from an unprocessed semen sample (Shirota *et al* 2016; Asghar *et al*, 2014; Tasoglu *et al* 2013). In semen samples from healthy male volunteers split into standard processing via centrifugation and swim-up procedure compared with microfluidic sperm sorting, a significantly higher percent motility and lower rate of sperm DNA fragmentation was detected with microfluidic sperm sampling (Shirota *et al* 2016). While the microfluidic sperm sorting technique has thus proven to be an efficient and reliable means of sperm preparation compared with the centrifugation and swim-up procedure, its use in clinical practice has not been rigorously studied. We aim to compare traditional preparation and microfluidic sperm sorting on assisted reproductive technology outcomes including oocyte fertilization and embryo quality in subjects electing to undergo in vitro fertilization for infertility.

Preliminary Studies:

The microfluidic sperm sorting device has been shown to isolate highly motile, morphologically normal, and high DNA integrity sperm from unprocessed human semen. We have utilized the microfluidic sperm chip to select sperm for intracytoplasmic sperm injection (ICSI) in 26 cases of patients with poor prior ART outcome after standard sperm processing and selection. In these poor prognosis cases, we had 73% fertilization rate and 59% good quality day 3 embryos. Furthermore, among those patients who have received an embryo transfer, 58% (7 out of 12) have had a positive pregnancy test. While we cannot compare these data statistically to the prior failed cycle (due to concerns regarding regression to the mean), these data compare favorably to age-matched controls. However, given that this is a highly selected population, we believe a randomized controlled trial is necessary to rigorously explore the utility of sperm selection with the microfluidic sperm chip.

Hypothesis:

Subjects randomized to sperm preparation by microfluidic sperm sorting will obtain higher quality day 3 embryos than those randomized to traditional sperm processing.

Study Aims:

- 1) Primary Aim: To compare day 3 embryo quality resulting from fertilization of oocytes by sperm selected by microfluidic sperm sorting compared to traditional sperm preparation methods.
- 2) Secondary Aim: To compare fertilization rates, blastulation rates, and pregnancy rates for subjects randomized to sperm selection by microfluidic sperm sorting compared to traditional sperm preparation methods.

Design:

This is a randomized controlled trial of couples undergoing in vitro fertilization for unexplained infertility. Couples will be randomized to sperm selection by the clinical standard of centrifugation

and density-gradient processing compared to the microfluidic sperm sorting chip. Subjects and investigators performing outcome assessment will be blinded to treatment assignment.

Inclusion Criteria:

The target population includes couples planning in vitro fertilization (IVF) with or without intracytoplasmic sperm injection for unexplained infertility at the UCSF Center for Reproductive Health with a history of poor embryo quality as defined by $\leq 40\%$ high quality D3 embryos in a prior IVF cycle. All eligible couples will be asked to join the study.

Exclusion Criteria:

Male partner with severe oligoasthenospermia (concentration $< 5 \times 10^6$ spermatozoa/mL; motility $< 10\%$)

Female partner with anovulation (PCOS, FHA)

Female partner age > 41

Female partner AFC < 7

Female partner with obstructed fallopian tubes (assessed in all patients prior to IVF)

Use of oocyte donor

Either Partner:

Cancer diagnosis in either partner

Any significant disease or psychiatric disorder that would interfere with consenting process

Treatment History:

History of > 1 prior cycle cancellation due to poor response

Treatment Plan:

Embryo co-culture

Use of adjunctive non-gonadotropin medications to improve embryo quality: growth hormone, sildenafil

Study Procedures:

Couples meeting eligibility criteria will be offered enrollment. Randomization will be performed by the study coordinator upon initiation of controlled ovarian stimulation. Neither study clinician nor subject will be aware of treatment allocation. Ovarian stimulation will be performed with standard treatment chosen by primary physician. The day of ovulation trigger will be determined by the primary physician. The andrology lab will be notified of allocation to conventional sperm preparation versus microfluidic sperm sorting on the day of ovulation trigger. Oocyte retrieval is performed 36 hours after ovulation trigger. On the day of oocyte retrieval, the male partner will produce a semen sample per usual clinic protocol. A semen analysis will be performed on all samples for assessment of volume, motility, concentration, and morphology prior to semen processing according to WHO criteria using a light microscope, consistent with usual clinic protocol. Following the semen analysis, the semen of those assigned to microfluidic sperm sorting will be pipetted into the inlet chamber of the sorting chip. The microfluidic sperm sorting device is a flow and chemical-free microfluidic single use "chip" with an inlet sample chamber connected to an outlet collection chamber by a microfluidic channel. The sorted sperm are collected from the outlet.

The semen of those assigned to standard processing will undergo conventional centrifugation and density gradient separation. ICSI or IVF will be performed by an embryologist blinded to treatment allocation with the processed sperm according to the primary physician's orders. After 16-18 hours, fertilization will be evaluated by the existence of two pro-nuclei. Fertilized embryos will be cultured to day 3 and evaluated by an embryologist blinded to treatment allocation for embryo quality. Cell number will be assessed in addition to blastomere symmetry and fragmentation (grade 1-6, highest quality to lowest). Those whose treatment plan involves a day 3 embryo transfer (determination made by primary physician) will undergo embryo transfer per clinic standard on day 3. Otherwise, embryos will be cultured to the blastocyst stage prior to

transfer. Blastocysts will be graded by Gardner Criteria, per clinic protocol. All women who undergo an embryo transfer will have a serum pregnancy test (beta HCG) 14 days later. Those with a positive serum test will repeat testing 48 hours later. Pregnancy ultrasounds will be scheduled at 5 weeks 5 days per clinic standard of care.

Device:

FERTILE: microfluidic sperm sorter

The device is labware. It is not an implant and is not purported to support or sustain human life. It is a flow and chemical free microfluidic single-use chip with an inlet chamber for receiving untreated semen samples and an outlet for collection of normal, healthy sperm for use in assisted reproductive technology procedures in andrology and embryology laboratories. It does not present any potential for serious risk to the health, safety, or welfare of participants.

Statistical Methods:

As this is a randomized controlled trial, known and unknown confounders are assumed to be evenly distributed between treatment groups. However, at the completion of enrollment, baseline characteristics will be assessed between groups and chi squared or t-tests will be performed, as appropriate to ensure groups are evenly distributed with respect to the most important clinical parameters such as age, duration of infertility, gravity/parity, prior infertility treatment, and ovarian reserve (AFC). The primary outcome, day 3 high quality embryo proportion will be defined as proportion of all viable embryos on day 3 with at least 6 cells and fragmentation/symmetry scores of 1-2. This proportion will be compared between groups with a t-test. An ANOVA will be performed to obtain and age and AFC-adjusted comparison of day 3 high quality embryo proportion between groups. Secondary outcomes will include fertilization and pregnancy rates. Fertilization rate will be defined as number of 2PN embryos per oocyte retrieved. Pregnancy rate will be defined as clinical pregnancy (ultrasound demonstrating gestational sac with yolk sac) per transfer. These secondary outcomes will be evaluated with a t-test.

References:

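### Semen quality is measured on every sample before processing, but the adjusted analysis contains no sperm variable, at a cost in precision rather than bias

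*Combined protocol and SAP*

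**What the plan says.** All references are to the Combined protocol and SAP.

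- **Measurement (Study Procedures).** "A semen analysis will be performed on all samples for assessment of volume, motility, concentration, and morphology prior to semen processing". This happens on the day of oocyte retrieval.
- **Baseline comparison (Statistical Methods).** Groups are compared on the "most important clinical parameters such as age, duration of infertility, gravity/parity, prior infertility treatment, and ovarian reserve (AFC"). No semen parameter is named.
- **Analysis (Statistical Methods).** The day 3 high-quality proportion is compared by t-test, and an ANOVA gives a comparison adjusted for age and AFC. Fertilization rate gets a t-test only. No stratification or subgroup is described.
- **Timing (Study Procedures).** "Randomization will be performed by the study coordinator upon initiation of controlled ovarian stimulation". Then: "The andrology lab will be notified of allocation to conventional sperm preparation versus microfluidic sperm sorting on the day of ovulation trigger".
- **Population (Design, Inclusion Criteria).** Design describes "couples undergoing in vitro fertilization for unexplained infertility", and Inclusion Criteria repeats the term: "The target population includes couples planning in vitro fertilization (IVF) with or without intracytoplasmic sperm injection for unexplained infertility". It is not defined.
- **Semen limit (Exclusion Criteria).** The only one is "Male partner with severe oligoasthenospermia", given as concentration below 5 million/mL and motility below 10%, with a semicolon between the two.

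**The concern.** The trial compares two ways of selecting sperm from a raw sample. The quality of that sample is a plausible predictor of fertilization and of day 3 embryo quality. The plan measures it on every couple before processing and then assigns it no named role. Both covariates in the adjusted comparison come from the list of age, history and ovarian reserve variables; none describes the sperm.

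Two things are at stake. Outcome variance that a measured covariate could remove stays in the error term. And a chance difference in semen quality between the arms would not be corrected, nor necessarily shown.

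A smaller matter is who is enrolled. An undefined diagnosis of unexplained infertility stands beside a semen exclusion that names only severe cases and can be read in two ways.

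**Working it through.** **1. What the documents supply.** They give no sample size, power, effect size, standard deviation or semen distribution. There is no figure to reproduce, and every number below that depends on one of these is an assumption.

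**2. Is the comparison biased without a semen term?** A simulation omitted a male factor present in 30% of couples that lowers the day 3 proportion by 0.15, with residual SD 0.28 and no treatment effect. There were 40,000 trials at each size. The factor's share of outcome variance is 0.15² × 0.3 × 0.7 / (0.15² × 0.3 × 0.7 + 0.28²) = 0.004725 / 0.083125 = 5.7%.

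| Couples per arm | Type I error of unadjusted t-test | Mean estimate |
|---|---|---|
| 25 | 5.2% | −0.0002 |
| 50 | 5.0% | −0.0007 |
| 100 | 5.0% | 0.0002 |

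The test keeps its level and the estimate centres on zero. Omission does not bias the result.

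**3. What is adjustment worth?** With n per arm = 2(1.960 + 0.842)² SD² / δ², a covariate that explains a share R² of the outcome variance otherwise left in the comparison multiplies n by (1 − R²). Assume δ = 0.15, SD = 0.30, two-sided 5% and 80% power: n = 2 × 7.849 × 0.09 / 0.0225 = 62.8, so 63 per arm.

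| R² assumed | n per arm with covariate | Power at that n without it |
|---|---|---|
| 5% | 62.8 × 0.95 = 59.6 → 60 | 78% |
| 10% | 62.8 × 0.90 = 56.5 → 57 | 76% |
| 20% | 62.8 × 0.80 = 50.2 → 51 | 71% |

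The proportional saving is about R² for any δ and SD. Against it, one covariate costs one degree of freedom, roughly 1/126 or under 1% at 63 per arm.

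**4. How likely is chance imbalance?** The exact binomial probability that the arms differ by 10 points or more in the share of couples with subnormal semen, for an assumed prevalence of 20% to 40%:

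| Couples per arm | Probability |
|---|---|
| 25 | 37–47% |
| 50 | 26–36% |
| 100 | 9–17% |
| 200 | 1.5–5% |

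Under the 0.15 effect assumed in step 2, a 10-point imbalance shifts the arm difference by 0.10 × 0.15 = 0.015, which is one tenth of δ = 0.15.

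**5. Eligibility wording.** A man with 3 million/mL and 40% motility is eligible if the two limits are joined by *and*, and excluded if they are joined by *or*. A man with 6 million/mL and 12% motility passes the exclusion on either reading. Whether he meets inclusion depends on what unexplained means, which is not stated.

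**The case against.** The strongest reply is that the analysis is valid as it stands. Statistical Methods relies openly on randomization to balance confounders, step 2 bears this out, and an adjusted comparison on two prognostic variables is already planned. Choosing a third covariate is partly judgement. The baseline list is introduced as examples, so semen parameters may still be tabulated. All of this stands, and it limits the point to precision and chance imbalance.

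Three stronger readings are tempting, and the documents support none of them.

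- *Male factor is left uncontrolled.* Randomization controls it in expectation.
- *The couples enrolled will not be those described.* Unexplained infertility is itself an inclusion term, so mixed male factor is possible but not established. Redundancy of the severe limit proves little, because Exclusion Criteria also lists anovulation and tubal obstruction, which the term would ordinarily rule out.
- *The benefit is expected only in men with poor semen and would be diluted.* Background/Significance argues that centrifugation itself causes DNA damage, and its split-sample comparison used healthy volunteers. That reasoning applies to ordinary semen too. Modification by motility is plausible, but the rationale does not predict it.

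A further objection concerns the covariate. The retrieval-day analysis follows randomization, in a lab that was told the allocation on trigger day. Processing cannot change the value, but a reader who knows the arm could. This stands, and the fix has to deal with it.

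**Conclusion.** The point holds as a missed gain in precision. Semen parameters are measured on all samples, and the adjusted comparison, which is limited to age and AFC, uses none of them. The unadjusted result is not biased by this. The size cannot be computed from the documents. It is about 5% to 20% of the sample size if semen covariates explain 5% to 20% of outcome variance, and negligible if they explain around 1% or less. Chance imbalance of 10 points or more is quite likely at 25 or 50 per arm and unlikely at 200, under the assumed prevalences, and its effect on the estimate would be modest.

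The undefined population term and the ambiguous semen limit are a secondary matter of clarification.

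**What to change.** 1. In Statistical Methods, prespecify pre-processing motility, or total motile count (volume × concentration × motility), as a covariate with age and AFC in the adjusted day 3 comparison. Add an adjusted comparison of the same form for fertilization rate.
2. Name pre-processing volume, concentration, motility and morphology in the baseline comparison.
3. Protect the covariate: record the semen analysis before the allocation is opened to the lab, or have it read by someone unaware of the arm. Alternatively, use the couple's pre-randomization semen analysis if one is on file.
4. Define unexplained infertility with respect to semen, reconcile it with the semen exclusion, and state how the two limits are joined.
5. A treatment-by-motility interaction is optional and, if included, should be labelled exploratory.

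The cost is one model degree of freedom, transfer of a routine lab value to the study dataset (the plan does not say that it is captured there), masking of one reading, and a few lines of eligibility wording.

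### IVF and ICSI couples are pooled, but insemination method is used neither in randomisation nor in analysis, which costs some precision and leaves no planned way to see whether the chip's effect differs by method

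*Combined protocol and SAP*

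**What the plan says.** All references are to the combined protocol and SAP.

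- **Inclusion Criteria.** The target population is "couples planning in vitro fertilization (IVF) with or without intracytoplasmic sperm injection for unexplained infertility". Both methods are eligible, with no quota.
- **Study Procedures, randomisation.** "Randomization will be performed by the study coordinator upon initiation of controlled ovarian stimulation". No stratification factor is named.
- **Study Procedures, insemination.** On retrieval day the semen is analysed, then prepared by the allocated method. After that, "ICSI or IVF will be performed by an embryologist blinded to treatment allocation with the processed sperm", and the choice between the two follows the primary physician's orders. The text does not say when the order is written or whether it may change once the prepared sample is available.
- **Study Procedures, blinding.** "Neither study clinician nor subject will be aware of treatment allocation". The inseminating embryologist is blinded too.
- **Statistical Methods.** The primary outcome, the proportion of high-quality day 3 embryos, is compared by an unadjusted t-test. The adjusted ANOVA uses age and AFC only. The baseline factors named do not include insemination method, although the list is given as examples. Secondary outcomes are compared by t-test. One fertilization definition serves both methods: "Fertilization rate will be defined as number of 2PN embryos per oocyte retrieved". No analysis by insemination method is planned.
- **Preliminary Studies.** "We have utilized the microfluidic sperm chip to select sperm for intracytoplasmic sperm injection (ICSI) in 26 cases of patients with poor prior ART outcome". No conventional-IVF results with the chip are given.

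**The concern.** The aims compare two ways of preparing sperm. What the prepared sample then does depends on the insemination method. In conventional IVF the whole prepared population meets the oocytes. In ICSI an operator picks a single sperm, in either arm. That second selection step could make the chip matter more under one method than the other. This is general reasoning, not something the documents state, and they give no basis for the size or direction of a difference.

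Two things are at stake. If method affects embryo quality or fertilization, leaving it out of design and analysis adds avoidable noise. And if the chip helps under one method only, the pooled estimate is a diluted average, with no planned analysis to show this. The investigators' own clinical experience with the chip does not settle the matter, because it covers one method only.

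**Working it through.** The plan states no sample size, SD, effect, alpha, power or ICSI share, so there is no figure to reproduce. Everything below illustrates scale under assumed inputs: SD of the couple-level proportion 0.30; effect 0.15 where the chip works; two-sided alpha 0.05; 80% power; 1:1 allocation.

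**1. Reference size.** n per arm = 2 × (1.96 + 0.842)² × 0.30² / 0.15² = 62.8, so 63. The standard error of the difference is 0.30 × √(2/63) = 0.053.

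**2. Dilution.** Let a share f of couples, those under one method, get no effect. The pooled effect is 0.15 × (1 − f), and power is Φ(pooled effect / 0.053 − 1.96). If those couples get half the effect, the pooled effect is 0.15 × (1 − f/2). The SD is held at 0.30.

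| f | Pooled effect (none in f) | Power at 63 per arm | n per arm for 80% | Power if half effect in f |
|---|---|---|---|---|
| 0 | 0.150 | 80% | 63 | 80% |
| 0.1 | 0.135 | 71% | 78 | 76% |
| 0.2 | 0.120 | 61% | 99 | 71% |
| 0.3 | 0.105 | 50% | 129 | 67% |
| 0.5 | 0.075 | 29% | 252 | 56% |

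**3. Chance imbalance.** The 95% range of the between-arm difference in ICSI share is ±1.96 × √(2p(1 − p)/63). That is ±0.14 at p = 0.2 and ±0.175 at p = 0.5. If method itself shifts the outcome by 0.05 to 0.20, the result moves by at most 0.14 × 0.05 = 0.007 to 0.175 × 0.20 = 0.035. Both are below one standard error, and this variation is already part of the t-test's error rate.

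**4. Precision lost.** The share of outcome variance due to method is m²p(1 − p)/0.30².
- With m = 0.05 and p = 0.2 it is 0.4%.
- With m = 0.10 and p = 0.5 it is 2.8%.
- With m = 0.20 and p = 0.5 it is 11%, which would shorten the confidence interval by 1 − √(1 − 0.111) = 6%.

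The gain is real but modest.

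**5. What an analysis by method could show.** With 63 per arm split evenly, each method has about 31.5 per arm. The standard error within a method is 0.30 × √(2/31.5) = 0.076, so the 95% half-width is 1.96 × 0.076 = 0.15. For the difference between the two effects the half-width is 1.96 × √2 × 0.076 = 0.21. This is enough to describe the effects, not to establish a moderate interaction.

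**6. Switching after processing, as a what-if.** Suppose the ICSI share came to differ by 10 to 30 points because of allocation, and method shifted the outcome by 0.10 to 0.20. The shift is 0.10 × 0.10 = 0.01 to 0.30 × 0.20 = 0.06. At 63 per arm, type I error for a pure preparation effect with method held fixed would be 5.4% to 20.2%. Nothing in the documents shows that such switching occurs.

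**The case against.** The strongest defence is that randomisation already does the work. Three stronger readings are tempting, and the documents do not support them.

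- **That chance imbalance confounds the result.** A reader might infer this because sizeable imbalance is common: at 50 per arm and a 50% ICSI share, the arms differ by 10 points or more in 37% of trials. But the t-test allows for that variation. The cost is precision, not validity.
- **That the arms will end up with different methods because of allocation.** A reader might infer this because the prepared sample is a product of the arm and the order is not fixed in advance. The text permits it but does not show it. Eligibility refers to couples already planning a method, and insemination "with the processed sperm according to the primary physician's orders" reads naturally as following a prior order. The semen analysis precedes processing in both arms, severe oligoasthenospermia is excluded, and the study clinician and embryologist are blinded. One gap remains: the text does not say whether the blinded study clinician includes the ordering primary physician. Even if a preparation did change the method used, that would be part of the effect of assigning it, and the comparison by assigned arm would remain valid for that effect.
- **That a null result would be uninterpretable.** It would still answer the pooled question posed by the Study Aims. It would not tell no effect apart from an effect under one method only.

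It is also fair to say that the baseline list is open-ended, that the fertilization denominator creates no problem of its own, and that the pilot, which the investigators say compares favourably with age-matched controls, gives no reason to expect that ICSI removes the effect.

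What stands is narrower: method is left out of randomisation and the adjusted model, and no analysis can show whether the effect differs by method.

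**Conclusion.** The point holds as a cheap improvement to the plan, not as an error that invalidates it. The main consequence is that a difference in effect between IVF and ICSI could go unseen and would dilute the pooled comparison. Under the assumed SD of 0.30, effect of 0.15 and 63 per arm, power falls from 80% to about 50% if 30% of couples get no benefit, and to 67% if those couples get half the benefit. The second consequence is lost precision: between 0.4% and 11% of outcome variance under the assumptions shown. The true size cannot be computed, because the documents give no sample size, SD, effect or ICSI share. Systematic bias from switching is a possibility that the text leaves open, not a finding.

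**What to change.** - Record the planned method (IVF or ICSI) before randomisation.
- Stratify randomisation by planned method, and carry it into the adjusted analysis. If stratification is not possible, add planned method as a covariate next to age and AFC for day 3 quality. Do the same for fertilization, which now has a t-test only and would need an adjusted analysis added.
- Analyse by planned, not performed, method. The performed method may be affected by allocation, so adjusting for it could remove part of the effect or introduce bias.
- Show the treatment effect by planned method as a descriptive secondary analysis with confidence intervals.
- Report changes from planned to performed method by arm. This describes any switching; neither it nor stratification removes the effect of switching.

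The cost is one form field, one design factor or model term, and an earlier statement of the intended method. The physician's freedom to change the method later is kept. Stratification and adjustment do not restore power lost to dilution; the analysis by method only makes such a difference visible, within the wide intervals shown above.

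### The primary outcome is a proportion of viable day 3 embryos, and no defined outcome measures survival from 2PN to day 3: report survival, per-2PN and per-oocyte results beside it

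*Combined protocol and SAP*

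**What the plan says.** Study Aims gives the primary aim as "To compare day 3 embryo quality resulting from fertilization of oocytes by sperm selected by microfluidic sperm sorting", against conventional preparation. Statistical Methods turns this into a proportion: "day 3 high quality embryo proportion will be defined as proportion of all viable embryos on day 3 with at least 6 cells" and fragmentation and symmetry graded 1 or 2. It is compared by t-test and by an ANOVA adjusted for age and AFC.

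The secondary aim is "To compare fertilization rates, blastulation rates, and pregnancy rates for subjects randomized to sperm selection by microfluidic sperm sorting". Statistical Methods defines two of these three outcomes: "Fertilization rate will be defined as number of 2PN embryos per oocyte retrieved" and "Pregnancy rate will be defined as clinical pregnancy (ultrasound demonstrating gestational sac with yolk sac) per transfer". Blastulation has no definition or denominator there.

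Under Study Procedures, couples are randomized when stimulation starts. The oocytes are later exposed to sperm prepared by the allocated method. "Fertilized embryos will be cultured to day 3 and evaluated by an embryologist blinded to treatment allocation for embryo quality". Couples planned for a day 3 transfer "will undergo embryo transfer per clinic standard on day 3. Otherwise, embryos will be cultured to the blastocyst stage".

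The document does not define *viable* and gives no rule for a couple with no viable embryo.

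**The concern.** The denominator is a set of survivors, and the sperm preparation may affect who survives. Background/Significance links sperm DNA damage to worse results, "including lower fertilization rates, impaired embryo progression, and decreased pregnancy rates", and reducing that damage is the reason for testing the chip. The trial's own rationale therefore makes an effect on the denominator plausible.

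No defined outcome covers the step in question. The fertilization rate stops at 2PN. The pregnancy rate starts at transfer. Blastulation is undefined, and culture to blastocyst is planned only where no day 3 transfer is planned.

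Two misreadings follow. An arm that loses more of its poor embryos before day 3 can show a higher proportion without producing more high-quality embryos. And an arm that loses good and poor embryos alike can match the other arm on both the primary and the fertilization rate while yielding fewer high-quality embryos.

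**Working it through.** The plan states no sample size, significance level, power or effect size, so there is no design figure to reproduce. What follows is an illustration.

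**Inputs from the document.** Fertilization F = 73% (Preliminary Studies). High quality = 40%, the eligibility ceiling for a prior cycle (Inclusion Criteria), used here per 2PN in A and per viable embryo in B.

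**Assumed.** Share v of 2PN embryos viable on day 3; Poisson oocyte counts with mean 10 (minimum 1); couple-level Dirichlet variation with ICC 0.1; one proportion per couple; two-sided t-test at 5%; 60 or 150 couples per arm; couples with no viable embryo dropped.

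**Identities.** With q = high quality per viable embryo (the primary): high quality per 2PN = v × q; high quality per oocyte = F × v × q.

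- **A, all extra losses are poor embryos.** Per 2PN is 0.40 in both arms; per oocyte is 0.73 × 0.40 = 0.292 in both. The primary is 0.40/v: 0.40/0.80 = 50.0%, 0.40/0.85 = 47.1%, 0.40/0.90 = 44.4%, 0.40/0.95 = 42.1%.
- **B, proportional losses.** q = 40% in both arms. Per 2PN is 0.80 × 0.40 = 0.32 v 0.95 × 0.40 = 0.38; per oocyte is 0.73 × 0.32 = 0.234 v 0.73 × 0.38 = 0.277.
- **Midway between A and B.** q = (50.0 + 40.0)/2 = 45.0% v (42.1 + 40.0)/2 = 41.1%.
- **C, more high-quality embryos lost.** Per 2PN is 0.28 v 0.38, so q = 0.28/0.80 = 35% v 0.38/0.95 = 40%.

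Percentage of simulated trials in which the t-test rejects, 60 / 150 per arm (4,000 runs; 3,000 for C):

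| Case | v | Primary, arm v arm | Primary | Fertilization rate | High quality per 2PN | High quality per oocyte | Survival 2PN to day 3 |
|---|---|---|---|---|---|---|---|
| A | 80 v 95 | 50.0 v 42.1 | 33.6 / 66.8 | 5.1 / 5.0 | 4.7 / 4.9 | 5.0 / 4.6 | 99.9 / 100 |
| A | 85 v 95 | 47.1 v 42.1 | 15.8 / 33.1 | 5.1 / 5.3 | 4.8 / 5.2 | 4.6 / 5.6 | 93.5 / 100 |
| A | 90 v 95 | 44.4 v 42.1 | 7.6 / 12.4 | 4.6 / 4.5 | 4.5 / 5.5 | 5.1 / 5.1 | 49.5 / 87.8 |
| Midway | 80 v 95 | 45.0 v 41.1 | about 12 / 21-23 | not run | not run | not run | not run |
| B | 80 v 95 | 40 v 40 | 5.1 / 5.5 | 5.1 / 5.1 | 24.6 / 52.8 | 22.1 / 48.7 | 99.8 / 100 |
| C | 80 v 95 | 35 v 40 | 17.0 / 34.2 | 5.0 / 5.2 | 60.1 / 92.9 | 56.1 / 90.8 | 99.9 / 100 |

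Repeat runs of A at 80% v 95% gave 32.5-33.7% and 65.3-66.9%. With ICC 0.2 or a mean of 7 oocytes, that case falls to 25-26% and 55-56%, and 90% v 95% to 6-7% and 10-11%.

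**Couples with no viable embryo.** They are 0.3-1.0% of couples at the base inputs and up to 3.0% in the sensitivity runs. Entering zeros instead of dropping them moves A at 80% v 95% from 33.6% to 31.6% and from 66.8% to 62.8%.

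**Limits of the per-oocyte measure.** Take 50% v 40% per viable embryo, fertilization 58.4% v 73%, and v = 95% in both arms. Per oocyte is then 0.584 × 0.95 × 0.50 = 0.277 v 0.73 × 0.95 × 0.40 = 0.277. It rejects in about 5%, while the primary rejects in 47% and 85%. With equal fertilization and viability, 50% v 40% is detected per oocyte in 43% and 82%, against 52% and 90% for the primary.

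**The case against.** The proportion answers the stated aim, which is embryo quality and not yield. Grading is blinded. Case A is an extreme: every extra lost embryo is a poor one, and viability, clustering, oocyte number and sample size are all assumed. The midway case and the 90% v 95% case are far milder. The direct measure of the gap is survival from 2PN to day 3; a per-oocyte result alone cannot separate survival from fertilization. All of this stands, except that blinding limits only differential judgement. It cannot remove a real effect of sperm preparation on survival, and the age and AFC adjustment does not address that either.

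Three stronger readings are tempting and not supported:

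- **The primary is biased in favour of the chip.** The Background rationale points the other way. If conventional processing loses more embryos, case A raises the conventional arm's proportion. Nothing in the document suggests that the chip loses more.
- **The undefined word alone decides the result.** At 80% v 95%, counting every 2PN embryo gives 40.0% v 40.0% instead of 50.0% v 42.1%. But that reading makes *viable* redundant. The genuine ambiguity is narrower, chiefly arrested embryos, and its effect has not been quantified.
- **The primary should give way to a per-oocyte outcome.** Per oocyte mixes fertilization with quality, can hide a quality effect and has lower power. Its merit is that its denominator is settled at retrieval, before any oocyte meets the prepared sperm. The per-2PN and per-viable denominators form afterwards.

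**Conclusion.** The point holds as a cheap improvement, not as a flaw that invalidates the primary. The plan conditions its primary outcome on survival to day 3 and defines nothing that measures that survival. A difference in survival could therefore move the primary at equal yield, or leave it unmoved when yield is lower, and the defined outcomes could not tell these apart.

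The documents do not give the size or direction. Under the assumed inputs, rejection of the primary at equal yield runs from near nominal (90% v 95% viable) to about one third or two thirds of trials (80% v 95%, all extra losses poor embryos, 60 or 150 per arm). It is much lower when losses are mixed, and the shift reverses when mainly good embryos are lost. The missing rule for couples with no viable embryo is minor, at about 0.3-3% of couples.

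**What to change.** Keep the planned primary. Before unblinding, add the following by allocated arm, with 95% confidence intervals:

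1. **Direct check:** survival from 2PN to viable day 3 embryo, and high-quality day 3 embryos per 2PN, beside the planned fertilization rate.
2. **Supporting analysis:** high-quality day 3 embryos per oocyte retrieved, scoring couples with oocytes but no 2PN or no viable embryo as 0.
3. **Couples without oocytes:** a count of high-quality embryos per randomized couple, with zeros for cancelled cycles and for couples with no oocyte, or at least the number of such couples by arm.
4. **Reading rule:** if the primary favours one arm, high quality per 2PN and per oocyte do not, and survival differs, do not conclude better embryo quality from the primary alone.
5. **Definitions:** whether arrested embryos count as viable, and how couples with no viable embryo enter the primary. The survival measure in item 1 depends on the first of these; the per-2PN and per-oocyte measures do not.

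The cost is an agreed laboratory definition and a few more analyses. Oocyte and 2PN counts and day 3 grades are already needed for the planned outcomes. Because per oocyte mixes fertilization with quality and has lower power, it accompanies the primary and does not replace it.
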